2.2 Safety

Safety of the test and reference products will be compared by evaluating the nature, severity and frequency of their adverse event profiles. All adverse events that occur during the study will be recorded whether or not they are considered to be related to the study medication. Descriptions of reactions or complaints will include the approximate date of onset, the date the adverse event ended, the severity of the adverse event, and the outcome. Comparisons between the treatment groups will be made by tabulating the frequency of subjects with one or more adverse events (classified into MedDRA terms) during the study. Pearson's Chi-Square test or Fisher's Exact test, whichever is most appropriate, will be used to compare the proportion of subjects in each treatment group with any adverse event. The adverse events reported by at least five percent of the subjects in any treatment group will be summarized descriptively.

[REDACTED]

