5.6 Safety Variables and Analyses

Duration of Treatment and Medication Compliance

Number of applications, days of exposure (i.e. duration of treatment), and compliance rate will be summarized by treatment group using descriptive statistics. For each subject, the duration of treatment (days) will be calculated using the following formula:

$(\text{Date of last application of study medication}) - (\text{Date of first application of study medication}) + 1.$

Medication compliance rate (%) will be calculated for each subject as follows:

$(\text{Total number of applications used}) / (\text{Expected number of applications}) * 100\%.$

[REDACTED] For prematurely discontinued subjects, expected number of applications will be determined based on the expected number of applications by the time of discontinuation, i.e. overall duration of treatment. Descriptive summaries of exposure and medication compliance rate will be provided by treatment group for the ITT subjects.

Adverse Events

Adverse events (AEs) will be coded in MedDRA, version 20.0. Treatment-Emergent Adverse Event (TEAE) is defined as any AE occurs on or after application of the first dose of study drug. Number and percent of subjects reporting TEAEs will be tabulated by treatment group. Summaries will be presented by body system and preferred term for the ITT population, and further by severity and relationship to study medication. TEAEs reported by 5% or more subjects for any treatment group will be summarized by preferred term. In the summaries of incidence rates (frequencies and percentages), severity and relationship to study drug, subjects who report more than one event that are mapped to the same preferred term will be counted only once under the strongest severity and relationship, accordingly. The difference between Test and Reference treatments with regard to severity and frequency of their dermatological adverse events will be statistically evaluated using Chi-Square or Fisher's exact test to compare the proportions of subjects of the two active treatment groups who report any TEAE.

Treatment-Emergent Serious Adverse Events (TESAEs) will be discussed within the clinical study report. TEAEs, TESAEs and TEAEs that led to treatment interruption or discontinuation will be presented in data listings.

Concomitant Medications and Vitals Signs

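### SAP 5.6 promises a statistical evaluation of dermatological AE severity and frequency, but the test it names is on any TEAE, which is neither limited to skin events nor graded by severity

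*SAP*

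**What the plan says.** The SAP's Adverse Events text in section 5.6 gives the purpose of the Test-Reference safety comparison as follows: "The difference between Test and Reference treatments with regard to severity and frequency of their dermatological adverse events will be statistically evaluated". The sentence goes on to name a chi-square or Fisher's exact test "to compare the proportions of subjects of the two active treatment groups who report any TEAE".

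Earlier in the same paragraph a TEAE "is defined as any AE occurs on or after application of the first dose of study drug". That definition is not restricted by body system or grade. Severity and body system enter only through tables: "Summaries will be presented by body system and preferred term for the ITT population, and further by severity and relationship to study medication".

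Protocol 2.2 sets a broader aim: "Safety of the test and reference products will be compared by evaluating the nature, severity and frequency of their adverse event profiles". Its test is Pearson's chi-square or Fisher's "Exact test, whichever is most appropriate", which "will be used to compare the proportion of subjects in each treatment group with any adverse event". Protocol 8.1.5 likewise judges the comparable safety of Test and Reference on the proportion reporting any adverse event. Neither protocol section, as far as it can be read, restricts the tested comparison to skin events or promises a test of severity.

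**The concern.** Purpose and test do not match within one SAP sentence. The purpose concerns two attributes (severity and frequency) of one class of events (dermatological). The test concerns one attribute (occurrence) of all events.

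Comparing the safety of the two gels is a study objective, and Protocol 7 lists local cutaneous irritation first among the reactions seen with the reference product. If the SAP is followed as written, the report could present the any-TEAE p-value as the answer on skin safety. A non-significant value would then be read as no difference in dermatological severity and frequency, which it does not test. A significant value could equally come from events that have nothing to do with the skin.

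**Working it through.** The readable text gives no AE rate, and the arm sizes are redacted, so there is no figure in the plan to reproduce. The check is a comparison of texts, followed by one example for scale.

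**Step 1. Question against variable**

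| Element | Stated purpose (SAP 5.6) | Named test (SAP 5.6) | Protocol 2.2 and 8.1.5 |
|---|---|---|---|
| Events | Dermatological AEs | Any TEAE | Any adverse event |
| Severity | Included | Not used | Not used in the test |
| Comparison | Test vs Reference | Test vs Reference | 8.1.5: Test vs Reference; 2.2: each treatment group |

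The second and third columns agree on the kind of variable; the SAP adds only the treatment-emergent restriction. The first column is the outlier.

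**Step 2. Consequences**

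- *Frequency.* Non-dermatological events enter both arms. A subject with such an event counts as a case whether or not a skin event also occurs, so a skin difference is diluted.
- *Severity.* If the arms have the same proportion with any TEAE but different grades, the test rejects only at its error rate, whatever the size of the severity difference.

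**Step 3. One example (every input assumed)**

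Inputs: 400 subjects per active arm; dermatological TEAE rates of 2% and 6%; a 10% rate of other TEAEs, equal in both arms and independent of skin events; two-sided Fisher's exact test; Newcombe 95% CIs.

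Dermatological TEAEs:
- 400 × 0.02 = 8 and 400 × 0.06 = 24.
- Difference 4.0 percentage points, 95% CI 1.3 to 6.9, p = 0.006.

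Any TEAE, with rate = 1 − (1 − background)(1 − dermatological rate):
- 1 − 0.90 × 0.98 = 0.118; 400 × 0.118 = 47.2, taken as 47.
- 1 − 0.90 × 0.94 = 0.154; 400 × 0.154 = 61.6, taken as 62.
- Difference 15/400 = 3.75 percentage points, 95% CI −1.0 to 8.5, p = 0.15.

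The SAP sentence would attach the second p-value to the first question. The example shows that the two analyses can part company. It does not predict that they will in this trial.

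**Step 4. What the AE data contain**

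Protocol 5.10 keeps the listed application site reactions (erythema, dryness, burning/stinging and so on) out of the AE record unless they lead to a temporary stop of medication, discontinuation from the study or a new concomitant medication. Dermatological TEAEs are therefore a filtered part of local tolerability. The 0 to 3 site reaction scores hold the rest, and the SAP compares them descriptively by visit.

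**The case against.** **The protocol's analysis is carried out.** Protocol 2.2 and 8.1.5 specify a test on any adverse event, and the SAP names that test. This stands. A reader might infer that the SAP replaces the protocol's safety test or omits one the protocol requires. The documents do not support that: the fault lies in the purpose the SAP gives the test.

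**Any TEAE may be shorthand for any dermatological TEAE.** The sentence is about dermatological events, so the reading is possible. However, the TEAE definition a few lines earlier has no such limit, and both protocol sections say any adverse event. Even on this reading only frequency would be covered, and severity would remain untested.

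**Redacted text might help.** There are redactions after the AE paragraph in Protocol 2.2 and in the synopsis safety row, and a definition of dermatological events could sit there. The absence of a definition can therefore be asserted only for the readable text. No redaction shows within the SAP paragraph itself, and hidden text elsewhere would not change what this sentence tests.

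**The tables already show skin events.** They do, by body system, preferred term and severity. A reader might go further and infer from the counting rule, under which events "mapped to the same preferred term will be counted only once under the strongest severity and relationship", that the tables cannot yield a count of subjects with any skin event. That over-reads the SAP. The rule concerns repeats of one preferred term; the SAP does not say how subjects are counted at body-system level, and no table shells are available.

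**The example rests on invented rates.** Correct. The mismatch is established by the text alone, and the example only shows its possible size.

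**Conclusion.** The point holds as a minor safety-analysis correction. SAP 5.6 assigns to an all-body-system, ungraded comparison a conclusion about dermatological severity and frequency that it cannot deliver. This is certain from the sentence and the TEAE definition beside it, and depends on no assumed number.

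Its practical size cannot be determined, because AE rates are not given and arm sizes are redacted. In the assumed example the p-value moves from 0.006 to 0.15; with other rates the gap could be larger or smaller.

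Two stronger conclusions might be drawn and should not be. The first is that a skin difference would go unseen: the TEAE tables and the site reaction scores would still display it. The second is that the equivalence or superiority findings are weakened: no efficacy analysis uses this test. What is at risk is one misattributed safety statement in the study report.

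**What to change.** Amend SAP 5.6 before unblinding; Protocol 8 already requires the SAP to be final by then.

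(a) Reword the sentence so that the chi-square or Fisher's exact test compares Test and Reference on the proportion of subjects with any TEAE, and state that this p-value supports no conclusion on dermatological severity or frequency.

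(b) To serve the purpose the SAP states:
- define dermatological TEAEs in MedDRA terms, for example the skin system organ class plus application-site preferred terms;
- report the Test-Reference difference in the proportion of subjects with at least one, with a 95% CI;
- report worst dermatological severity per subject, taken across all such terms, as an estimate with a CI and no test;
- interpret both alongside the graded application site reaction scores, because of the recording rule in Protocol 5.10.

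**Cost.** Part (a) changes one sentence and adds no analysis. Part (b) needs one definition and two table rows from data already coded and graded. Its downside is one or two further unadjusted safety comparisons, with wide intervals, above all for severity.

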6.1 Handling of Missing or Incomplete Dates for Adverse Events and Concomitant Medications

Adverse Events

Handling of partial dates is only considered for the start date. An adverse event with a partial start date is considered treatment emergent if:

- only the day is missing and the start month/year is the same or after the month/year of the first dose
- the day and month are missing and the start year is the same or greater than the year of the first dose date
- the start date is completely missing

Concomitant Medications

Handling of partial dates is only considered for the stop date. A medication with a partial stop date is considered concomitant if:

- only the day is missing and the stop month/year is the same or after the month/year of the first dose
- the day and month are missing and the stop year is the same or greater than the year of the first dose date
- the stop date is completely missing or the medication is ongoing

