7.2 Definitions

An adverse event (AE) is defined as any untoward medical occurrence in a subject administered a medicinal product and which does not necessarily have to have a causal relationship with this treatment. An adverse event can therefore be any unfavorable and unintended sign (for example, an abnormal laboratory finding), symptom, or disease temporally associated with the use of a medicinal product, whether or not considered related to this medicinal product.

A serious adverse event (SAE) is an adverse event that results in any of the following outcomes:

- Death
- Life-threatening event (e.g., the subject was, in the opinion of the investigator, at immediate risk of death from the event as it occurred. It does not include an event that, had it occurred in a more severe form, might have caused death)
- Requires in-subject hospitalization or prolongs hospitalization
- A persistent or significant disability/incapacity or substantial disruption of the ability to conduct normal life functions
- Congenital anomaly/birth defect
- Other adverse events that may be considered serious based upon appropriate medical judgment, may jeopardize the subject and may require medical or surgical intervention to prevent one of the outcomes listed above.

Immediately Reportable Adverse Events (IRAE): Any serious AE or any AE that necessitates discontinuation of study medication, including pregnancy.

Unexpected Adverse Event: An unexpected event is any adverse drug experience, the specificity or severity of which is not consistent with the current approved product labeling (package insert) for the study medication, the Investigator's Brochure, or as described in the clinical protocol and consent materials.

Intensity of Adverse Events: The maximum intensity of an AE during a day should be recorded on the CRF. If the intensity of an AE changes over a number of days, then separate entries should be made having distinct onset dates for the changes in severity.

Mild - AEs are usually transient, requiring no special treatment, and do not interfere with subject's daily activities.

Moderate - AEs typically introduce a low level of inconvenience or concern to the subject and may interfere with daily activities, but are usually ameliorated by simple therapeutic measures.

Severe - AEs interrupt a subject's usual daily activity and traditionally require systemic drug therapy or other treatment.

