7.3 Eliciting and Reporting of Adverse Events

The investigator will periodically assess subjects for the occurrence of adverse events. In order to avoid bias in eliciting adverse events, the subject or parent/legally authorized representative should be asked a non-specific question (e.g., “How have you been feeling since your last visit?”) to assess whether any AE has been experienced since the last visit. All adverse events (as defined in [Section 7.2](#)), either observed by the Investigator or one of his/her medical collaborators, or reported by the participant spontaneously, or in response to direct questioning, will be reported and documented in the source document and the study reporting forms. When reporting an adverse event, the Investigator must assign a severity grade to each event and declare an opinion on the relatedness of the event to the study medication or procedure. Serious or unexpected adverse events must be reported to Perrigo **within 24 hours** of when the Investigator first learns of the occurrence of the event.

Adverse events will be documented in the source document and recorded in a timely manner on the eCRFs. Adverse events (e.g., worsening of acne*) that are identified at the last assessment visit (or the early termination visit) must be recorded on the AE eCRF with the status of the AE noted.

Adverse event reporting begins from the signing of informed consent/assent. Adverse events should be followed until resolved or 30 days after the final study treatment. In any case, serious adverse events that are not resolved or considered to be chronic within 30 days of the final study treatment must be followed by the investigator until they become resolved or are considered to be chronic (stabilized for at least 30 days). All events that are ongoing at this time will be recorded as ongoing on the eCRF.

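### SAP 6.1 classes an adverse event known to have ended before the first dose as treatment-emergent when its start date is missing, or partial and in the month or year of first dose

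*SAP*

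**What the plan says.** SAP 5.6 gives the definition: "Treatment-Emergent Adverse Event (TEAE) is defined as any AE occurs on or after application of the first dose of study drug". It contains no condition on the stop date and no provision for an event already present that worsens.

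SAP 6.1 covers incomplete dates. For adverse events, "Handling of partial dates is only considered for the start date", and the event is treatment-emergent in any of three situations:

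- A start without its day counts if "only the day is missing and the start month/year is the same or after the month/year of the first dose".
- A start known only by its year counts if that year equals or follows the year of dosing.
- A start of which nothing is recorded always counts.

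Three parts of the protocol bear on how these rules operate. Protocol 7.3 sets the start of collection: "Adverse event reporting begins from the signing of informed consent/assent". Protocol 2.2 lists the end date among the items recorded for each event. Protocol 7.2, on intensity, says that "separate entries should be made having distinct onset dates for the changes in severity", and does not limit this to worsening.

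The classification feeds the comparison at the end of the Adverse Events part of SAP 5.6, where the proportions of Test and Reference subjects with any TEAE are compared by a chi-square or Fisher's exact test.

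**The concern.** Treating an event of uncertain onset as treatment-emergent is a sensible default. It stops being sensible when another recorded date settles the question. An event that ended before the first dose cannot have begun on or after it, whatever is missing from its start date. SAP 6.1 still classes such an event as a TEAE if it meets one of the three bullets, because the stop date is never consulted.

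The secondary point is a gap between two documents. The protocol's recording rule creates a new entry with a new onset date when an event eases as well as when it worsens. The SAP does not say whether the unit of classification is the entry or the episode, and each choice has a fault:

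- By entry, a pre-dose event that only improves after dosing acquires a post-dose onset and becomes a TEAE.
- By episode, with the onset of the episode, a pre-dose event that truly worsens after dosing is lost, because SAP 5.6 has no worsening criterion.

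At stake is the any-TEAE proportion, the safety measure that the SAP tests between Test and Reference; application site reactions are compared only descriptively. Errors that fall equally on randomized arms raise both rates and pull them together. That favours a finding of comparable safety.

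**Working it through.** The plan states no figure on this point, and the sample size and allocation are redacted, so there is nothing to reproduce. The check has two parts.

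**1. The rules applied to test events.** Assume a first dose on 20 March 2018. The dates test the logic only and are not meant to be typical. The last column adds one condition: not a TEAE if the known stop date is before the first dose.

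| Event | As written | With stop-date check |
|---|---|---|
| Start 10 March, stop 15 March | not TEAE | not TEAE |
| Start March 2018, day missing; stop 15 March | **TEAE** | not TEAE |
| Start February 2018, day missing; stop 15 March | not TEAE | not TEAE |
| Start 2018, day and month missing; stop 15 January | **TEAE** | not TEAE |
| Start wholly missing; stop 15 January | **TEAE** | not TEAE |
| Moderate from 10 March to 24 March (first entry) | not TEAE | not TEAE |
| Same event, eased to mild from 25 March (second entry) | **TEAE**, if entries are separate events | **TEAE**, on the same condition |

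The stop-date check corrects all three wrong results among events that ended before dosing. It does not touch the eased event, which needs a linkage and worsening rule. The SAP 5.6 rule that counts a subject once per preferred term, at the strongest severity, does not help either, because it acts after TEAE status has been assigned.

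**2. Effect on the comparison, by assumption only.** Let *p* be the true any-TEAE rate in an arm and *q* the share of TEAE-free subjects wrongly counted, equal in both arms. The reported rate is *p* + (1 − *p*)*q*, so the difference between arms is multiplied by (1 − *q*).

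None of the following inputs is in the documents: 400 subjects per active arm, true rates of 12% and 18%, and *q* from 0 to 5%. Power is for a two-sided 0.05 test by the normal approximation, with pooled variance under the null.

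| *q* | Reported rates | Difference | Risk ratio | Power |
|---|---|---|---|---|
| 0 | 12.00% and 18.00% | 6.00 points | 1.50 | 66% |
| 1% | 12.88% and 18.82% | 5.94 points | 1.46 | 63% |
| 2% | 13.76% and 19.64% | 5.88 points | 1.43 | 61% |
| 5% | 16.40% and 22.10% | 5.70 points | 1.35 | 53% |

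For example, at *q* = 1%: 0.12 + 0.88 × 0.01 = 0.1288, 0.18 + 0.82 × 0.01 = 0.1882, and 0.1882 − 0.1288 = 0.0594. The table shows direction and shape. It does not estimate *q*.

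**The case against.** The strongest reply is that very few events can be affected. The first listed visit is Visit 1/Day 1. Protocol 5.13 puts consent and eligibility before randomization, and Protocol 5.11 and 5.16 have the first dose applied on site on Day 1. If consent is given that day, an event has only hours in which to begin and end before dosing. Protocol 11.1 also provides source verification and queries for missing data, so incomplete dates on such recent events should be uncommon. This largely stands. The window is not certain, however: Protocol Section 9 requires consent before any medication withdrawal done for the research and mentions a screening phase, while the visit details are redacted.

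A second reply is that counting doubtful events is conservative. That holds when the onset is truly unknown, but not when the stop date resolves it.

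A third is that Protocol 2.2 and 8.1.5 compare subjects with any adverse event, treatment-emergent or not. That is so, but the SAP's test uses TEAEs, and a TEAE count should contain only treatment-emergent events.

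Two stronger readings are tempting, and the documents do not support them:

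- A reader might infer that events which ended before dosing count as TEAEs in general. They do not. SAP 5.6 excludes those with a complete pre-dose start date, and SAP 6.1 excludes a missing-day start in a month before that of first dose.
- A reader might infer that the SAP itself makes every severity change a new TEAE. The new onset date comes from a recording instruction in Protocol 7.2, which can be read as one event with several entries. The SAP neither says that each entry is a separate event nor rules it out.

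**Conclusion.** The main point holds in a narrow form. By its own terms, SAP 6.1 misclassifies an adverse event known to have ended before the first dose when its start is missing, or is partial and falls in the month or year of first dose. This follows from the text without assumptions.

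The severity point is a gap to close rather than a stated error. The false TEAE arises only if entries are analysed one by one.

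The direction is a slight inflation of TEAE rates and a dilution of the Test-Reference difference, provided that the errors are similar across randomized arms. The size cannot be derived, since the documents give no rate of pre-dose events or of incomplete dates; it is probably very small. A reader who takes any row of the second table with *q* above zero as the expected loss would go beyond the evidence. No efficacy or equivalence analysis is affected. This is a worthwhile correction, not a threat to the trial's conclusions.

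**What to change.** In SAP 6.1, under Adverse Events, add: *An event whose known stop date (or partial stop date that can only be earlier) is before the first dose is not treatment-emergent, whatever its start date.* The opening statement that only the start date is considered should be amended to match. The same section already uses stop dates to classify concomitant medications, so the logic is familiar.

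In SAP 5.6, state that entries recording severity changes of one episode are linked and carry the onset of that episode. Define a TEAE as an event with onset on or after the first dose, or an event already present that worsens after the first dose.

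The cost is a few sentences and a link field or programming step. End dates are already collected, so nothing more is asked of subjects. The change should be made before the blind is broken.
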